6.2 Visit 3: 3 Month Visit (+/- 30 day window)

The coordinator will request that the subject refrain from smoking for 12 hours prior to the study visit.

The subject will arrive at the study site outpatient clinic. The following procedures will be performed:

- Labs/Phlebotomy: complete blood count with differential, including hemoglobin, hematocrit, and platelet count, complete metabolic panel, and coagulation studies, lipid panel, estradiol, progesterone, testosterone, sample for storage for future studies; stored samples will only apply to the 10 Mayo participants.
- Arterial blood gas (while seated while breathing room air)
- Review of medical history
- Review current medications
- Vital signs
- Physical exam
- Modified Medical Research Council Dyspnea Scale assessment
- Dispense supply of study drug (3 month supply to be given at this visit)
- Reinforce instructions on recording of new medications and dose changes
- Reinforce instructions on bringing the subject's routine and study medications to all visits

Blood samples for study assays will be processed and/or banked.

The investigator or research coordinator will take an interim medical history and perform a physical examination including vitals, review current medications, and complete the mMRC Dyspnea Scale assessment. A pre-packaged 3 month supply of study medication (encapsulated letrozole 2.5 mg or placebo capsules) will be prepared for the subject by the Research Pharmacy. Subjects will again be instructed on the proper administration of the study medication.

Once instruction has been given to the subject and the subject expresses understanding, the research coordinator will thank the subject for their attendance and reinforce compliance with the study medication and protocol. The coordinator will contact the clinician 24 hours after the study visit to discuss the clinical lab results.

6.3 Visit 4: 6 Month Visit (+/- 30 day window)

The research coordinator will remind the subject to avoid heavy exercise for 12 hours prior to the study visit. The coordinator will also request that the subject refrain from smoking for 12 hours prior to the study visit.

The subject will arrive at the study site outpatient clinic. The following procedures will be performed:

- Labs/Phlebotomy: complete blood count with differential, including hemoglobin, hematocrit, and platelet count, complete metabolic panel, and coagulation studies, lipid panel, estradiol, progesterone, testosterone, sample for storage for future studies; stored samples will only apply to the 10 Mayo participants.
- Arterial blood gas (while seated while breathing room air)
- Technetium macroaggregated albumin perfusion scan

- Review of medical history
- Review current medications
- Vital signs
- Contrast echocardiogram
- Physical exam
- Modified Medical Research Council Dyspnea Scale assessment
- SF-36 questionnaire assessment
- 6 minute walk distance with Borg Score

Blood samples for study assays will be processed and/or banked.

After all these studies have been completed, the investigator or research coordinator will take an interim medical history and perform a physical examination including vitals, review current medications, and complete the mMRC Dyspnea Scale assessment.

The research coordinator will thank the subject for his or her participation. The coordinator will contact the clinician 24 hours after the study visit to discuss the clinical lab results.

Test	Baseline	1 month	3 months	6 months
History	X	X	X	X
Modified Medical Research Council (mMRC) Dyspnea Scale	X	X	X	X
Assessment of adverse effects-		X	X	X
Assessment of compliance		X	X	X
Physical examination, including vital signs	X	X**	X	X
Room air arterial blood gas in seated position	X		X	X
Laboratory Data*	X		X	X
SF-36	X			X
Contrast-enhanced echocardiogram	X			X
Technetium macroaggregated albumin perfusion scan	X			X
6 minute walk distance with Borg Score at baseline and completion	X			X
Complete pulmonary function tests if not performed within 3 years (spirometry, lung volumes and diffusion capacity)	X			
DEXA Scan	X			
Dispense study medication	X		X	

* Laboratory data to include complete blood count, complete metabolic panel, lipid panel, PT/INR, estradiol, progesterone and testosterone levels and stored samples for future analysis.

** If in-clinic visit

7 Assessment of Efficacy and Outcome Measures

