5.2 Treatment Regimen

Subjects will take 2.5 mg of Letrozole or an identical placebo by mouth daily for 6 months.

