5.4 Preparation and Administration of Study Drug

Letrozole and placebo tablets will be over-encapsulated by the Research Pharmacy both at the Mayo Clinic and at the University of California, San Francisco. At the Research Pharmacy, capsules will be packaged into identical bottles with a liner, cotton, and childproof cap. Bottles will be labeled to meet state and FDA requirements. There will be two visits during which the drug will be administered. At the (Baseline), subjects will receive a 3-month supply; and at their 3 month, (Month 3) subjects will receive a 3-month supply of drug.

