6.1 Study Visits

6.1.1 Informed Consent

Eligible subjects meeting the inclusion/exclusion criteria will be referred if there is interest in enrolling. The following procedures will be performed during the screening process:

- Sign and date the informed consent and HIPAA release
- Review of the inclusion/exclusion criteria
- Schedule a screening visit

After the subject has consented, the subject will be scheduled for a baseline visit within 60 days. If the baseline visit is not scheduled within the first 2 weeks following the informed consent, the research coordinator will send a reminder letter to the subject. The coordinator will also request that the subject refrain from smoking for 12 hours prior to the study visit. Visit 1: Baseline

Baseline information will be used to characterize the participants and to compare the experimental groups with regards to demographics and other variables. Safety laboratories, ABG, and contrast TTE obtained at the screening visit will be used as baseline measurements. Eligibility criteria will be reviewed prior to randomization to treatment group.

The research coordinator will remind the subject to avoid heavy exercise for 12 hours prior to the study visit. The coordinator will also request that the subject refrain from smoking for 12 hours prior to the study visit.

The following procedures will be performed within 60 days of consent, during the baseline visit and after evaluation of this data, the investigator will determine they are eligible to enroll in the trial:

- Review of inclusion/exclusion criteria
- Labs/Phlebotomy: complete blood count with differential, including hemoglobin, hematocrit, and platelet count, complete metabolic panel, and coagulation studies, lipid panel, estradiol, progesterone, testosterone, sample for storage for future studies; stored samples will only apply to the 10 Mayo participants. Values can be obtained from last 90 days
- Arterial blood gas (while seated while breathing room air) Values can be obtained from last 90 days.
- Spirometry and lung volumes (if not performed within the prior 3 years)
- Contrast echocardiogram. Values can be obtained from last 365 days.
- Technetium macroaggregated albumin perfusion scan Values can be obtained from last 365 days.
- DEXA scan Values can be obtained from last 365 days.
- Review of medical history
- Review current medications
- Vital signs
- Physical exam Values can be obtained from last 90 days.

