6.1.2 Visit 2: 1 Month Visit (+/- 30 day window)

This visit may be done via telemedicine if agreed upon by both provider and study subject. Subjects will still be instructed to bring their routine and study medications with them to each visit.

The subject will arrive at the study site outpatient clinic. The following procedures will be performed:

- Interim medical history
- Vital signs (if in-clinic visit)
- Physical exam (if in-clinic visit)
- Review current medications
- Study drug accountability
- Assessment of adverse effects
- Modified Medical Research Council Dyspnea Scale assessment
- Reinforce instructions on recording of new medications and dose changes
- Reinforce instructions on bringing the subject's routine and study medications to all visits

The investigator or a nurse will take an interim medical history and perform a physical examination including vitals (if in-clinic visit), review current medications, and complete the mMRC Dyspnea Scale assessment. Coordinator or other study staff will ensure subject has enough drug to reach 3-month time point. Subjects will again be instructed on the proper administration of the study medication.

Once instruction has been given to the subject and the subject expresses understanding, the research coordinator will thank the subject for their attendance and reinforce compliance with the study medication and protocol.

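### A window-compliant primary 6-month blood gas can fall up to about 30 days after the dispensed drug runs out, and nothing ties it to the last dose

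*Combined protocol and SAP*

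**What the plan says.** Section 5.2 sets the regimen: "Subjects will take 2.5 mg of Letrozole or an identical placebo by mouth daily for 6 months". Section 5.4 provides for two dispensing visits: at baseline "subjects will receive a 3-month supply; and at their 3 month, (Month 3) subjects will receive a 3-month supply of drug". Section 6.2 repeats this for the month-3 visit ("Dispense supply of study drug (3 month supply to be given at this visit"), and the schedule table in Section 6.3 marks dispensing at baseline and 3 months only.

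The ABG for the primary endpoint is drawn at "Visit 4: 6 Month Visit (+/- 30 day window". The second dispensing visit has a window of the same width: "Visit 3: 3 Month Visit (+/- 30 day window". One passage checks supply against a later visit, at month 1 (Section 6.1.2): "Coordinator or other study staff will ensure subject has enough drug to reach 3-month time point". There is no counterpart for month 6. Section 8.4.3 tests the change from baseline to 6 months with a two-sample t-test. Neither it nor Section 7.1.1 mentions time since last dose.

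On the baseline value, Section 6.1.1 (which runs on into Visit 1) says: "Safety laboratories, ABG, and contrast TTE obtained at the screening visit will be used as baseline measurements". The list of baseline-visit procedures in the same section then has: "Arterial blood gas (while seated while breathing room air) Values can be obtained from last 90 days".

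**The concern.** Section 1.1 gives the aim as the effect on the A-a gradient of 6 months of letrozole. The visit window extends a month beyond the point at which the dispensed drug would be used up. A subject who takes every capsule and attends within the window can therefore have the primary measurement after some weeks without drug. If the gradient drifts back off treatment, such a value understates the effect that the trial is meant to measure. With 10 subjects per arm, a few such values could matter.

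Separately, the primary change score needs one baseline value per subject. Section 6.1.1 can be read as pointing to the screening ABG, to an ABG at the baseline visit, or to an earlier one, with no order of precedence and no stated date from which the look-back is counted.

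**Working it through.** **Stated power.** Section 8.2 claims 80% power for 13.2 mmHg with SD about 10 mmHg and 20 subjects. With 10 per arm, two-sided α = 0.05 and 18 degrees of freedom, the noncentrality is 13.2 / (10 × √(2/10)) = 2.95, and the exact t-test has power 79.7%. The figure reproduces and is not disputed.

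**Inputs.** From the documents: two supplies of 3 months; Visit 3 at 3 months ± 30 days; Visit 4 at 6 months ± 30 days. Assumed, because not stated: 30-day months, windows counted from the baseline visit, first dose on day 0, *n* = 90 capsules per supply, full adherence. Visit 3 then falls on days 60–120 and Visit 4 on days 150–210.

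**End of supply.** Supply ends at max(2*n*, V3 + *n*), where V3 is the day of Visit 3. The gap is 210 minus that day for a visit on the last permitted day. Days without supply before Visit 3 are max(0, V3 − *n*).

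| Visit 3 (day) | Days without supply before Visit 3 | Supply ends (day) | Gap at day 210 |
|---|---|---|---|
| 60 | 0 | 180 | 30 |
| 90 | 0 | 180 | 30 |
| 100 | 10 | 190 | 20 |
| 110 | 20 | 200 | 10 |
| 120 | 30 | 210 | 0 |

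In every row the two gaps add up to 30 days. A late Visit 3 moves the uncovered time to before Visit 3 and its 3-month ABG (a secondary endpoint), unless the month-1 check leads to extra supply.

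**Sensitivity to the assumptions (Visit 4 on its last permitted day).**
- Capsules per supply: 93 gives 210 − 186 = 24 days. 84 gives 210 − 168 = 42 days if Visit 3 is by day 84, or 210 − 174 = 36 if it is on day 90.
- Adherence *a*, Visit 3 on time, unused capsules kept: supply ends at 180/*a*. At 95% that is day 189.5, gap 20.5. At 90% it is day 200, gap 10. At 85.7% it is day 210, gap 0.
- First dose delayed by 3, 7 or 14 days: gap 27, 23 or 16 days.
- Visit 4 counted from an on-time or late Visit 3 instead of from baseline: (V3 + 120) − (V3 + 90) = 30 days.

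**Drug level.** On the 2-day half-life in Section 1.3, 30 days is 15 half-lives, leaving 2⁻¹⁵ = 0.003%. If that section's 2–6 weeks to steady state is read as five half-lives (assumption), the half-life is 2.8–8.4 days and 0.06–8.4% remains. This describes drug level, not AaPO₂.

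**Interval between the two primary ABGs.** Counting the look-back from the baseline visit: minimum 0 + 150 = 150 days, maximum 90 + 210 = 300 days.

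**The case against.** Supply equals regimen: 6 months are prescribed and 3 + 3 months are dispensed. A subject seen on day 210 has completed the prescribed course, and the ± 30 days is an ordinary visit window. That is true, and a reader who infers that the supply contradicts the regimen goes too far. But it does not stop the primary measurement from falling off drug, because nothing links the ABG to the last dose.

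The 30-day figure also stacks favourable assumptions: exact capsule count, no overage, immediate first dose, full adherence, Visit 3 on time or early, Visit 4 on its last day. This stands, and the figure is a limit only. Of the 61 permitted days, 30 (days 181–210) lie after supply ends, and a reader might infer that about half of the visits will be off drug. The documents say nothing about where in the window visits will fall.

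A reader might also infer a loss of power. That cannot be supported. The documents do not say how many subjects would be measured late or whether AaPO₂ reverts off drug, and the planning SD of about 10 mmHg may already include variation in timing.

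For the baseline ABG, counting 90 days back from consent, with the baseline visit up to 60 days later, would stretch the maximum interval to 90 + 60 + 210 = 360 days. The allowance is attached to a baseline-visit procedure, so counting from that visit is the natural reading and 300 days is the fair limit.

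**Conclusion.** The concern holds as a gap in measurement timing. On the assumptions listed, a fully adherent subject with Visit 3 on time or early can have a window-compliant primary ABG up to about 30 days after supply ends. The limit is 24 or 42 days with 93 or 84 capsules per supply, and it shrinks with missed doses. A late Visit 3 relocates the uncovered time and does not remove it.

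Both arms follow the same rule, so there is no type I error problem and no bias favouring an arm. What remains is possible dilution of the on-treatment 6-month effect, of unknown size. The text settles that the gap is permitted; it does not settle how often it would occur or what it would do to AaPO₂. The change is worth making because it is cheap, not because harm has been shown. The baseline wording is a minor clarification.

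**What to change.** 1. Reconcile the Visit 4 window (Section 6.3) with the regimen and dispensed supply (Sections 5.2, 5.4 and 6.2). No supply or dosing rule is proposed here.
2. Within the existing window, schedule the primary ABG as close to month 6 as possible while supplied drug still covers the subject.
3. Keep any later ABG in the primary analysis. A late value is still a 6-month value, so no subject is lost under the intent-to-treat rule (Section 8.4.1) or the completers analysis (Section 8.4.5).
4. Record days from last dose to the ABG, using the pill logs already planned in Section 5.5, and report them by arm descriptively. With 10 per arm, a formal comparison by this post-randomization variable would tell little.
5. In Section 6.1.1, state one baseline rule: the last ABG before the first dose, with the look-back counted from the baseline visit.

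The cost is less scheduling slack: with Visit 3 on time or early, and on the assumptions above, the target is days 150–180 of a window that runs to day 210. Some subjects would have slightly under 6 months of exposure at the measurement. No extra baseline ABG is needed.

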Study Design	Randomized, double-blind, placebo-controlled parallel trial of 20 subjects with HPS. Eligible subjects will be randomly assigned 1:1 to receive either letrozole 2.5 mg orally daily or placebo for 6 months.
Number of Subjects	20 total subjects; 10 subjects at each site
Duration of Administration	6 months
Reference therapy	There is no reference therapy

Statistical Methodology	
Primary endpoint:
 
 • Difference in changes in AaPO₂ between letrozole and placebo groups at 6 months. 
Secondary endpoints:
 
 • Difference in changes in intrapulmonary shunting between letrozole and placebo groups at 6 months • Difference in changes in estradiol, progesterone, testosterone levels between letrozole and placebo groups at 3 months and 6 months • Difference in changes in SF36 scores and mMRC dyspnea scale scores between letrozole and placebo groups at 6 months • Difference in changes in distance walked in six minutes between letrozole and placebo groups at 6 months • Difference in changes in PaO₂ and oxygen saturation by pulse oximetry between letrozole and placebo groups at 3 months and 6 months • To assess the effect of letrozole versus placebo on AaPO₂ at 3 months and 6 months • Safety and side effects associated with letrozole administration in patients with HPS 
Sample size and power:
 
A total of 20 patients will be enrolled (10 letrozole, 10 placebo), which will provide 80% power to detect a 13.2 mm Hg difference in changes in AaPO₂ ($\alpha = 0.05$).
 
Data analysis:
 
The primary analysis will compare the absolute change from baseline to 6 months in AaPO₂ between the blinded treatment arms using a two-sample t-test. Incidence of adverse events and secondary endpoints will also be analyzed.

-------------------------	---

1 Introduction

This document is a protocol for a human research study. This study will be carried out in accordance with the applicable United States government regulations as well as research policies and procedures of both Mayo Clinic and the University of California, San Francisco.

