3.3 Duration of Participation

Subjects will participate for 6 months.

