9.3.3 Interpretation of Definitions

AE Reporting Period

The study period during which AEs must be reported is normally defined as the period from the initiation of any study procedures to the end of the study treatment follow-up. For this study, the end of study treatment follow-up is Week 14.

Pre-existing Condition

A pre-existing condition is one that is present at the start of the study. A pre-existing condition should be recorded as an AE if the frequency, intensity, or the character of the condition worsens during the study period.

General Physical Examination Findings

At screening, any clinically significant abnormality should be recorded as a pre-existing condition. At the end of the study, any new clinically significant findings/abnormalities that meet the definition of an AE must also be recorded and documented as an AE.

Post-Study AE

All unresolved AEs considered possibly, probably or definitely related to the study drug should be followed by the investigator until the events are resolved, the subject is lost to follow-up, or the AE is otherwise explained. At the last scheduled visit, the investigator should instruct each subject to report any subsequent event(s) that the subject, or the subject's personal physician, believes might reasonably be related to participation in this study. The investigator should notify the study sponsor of any death or AE occurring at any time after a subject has discontinued or terminated study participation that may reasonably be related to this study. The sponsor should also be notified if the investigator should become aware of the development of cancer or of a congenital anomaly in a subsequently conceived offspring of a subject that has participated in this study.

Abnormal Laboratory Values

A clinical laboratory abnormality should be documented as an AE if any one of the following conditions is met:

- The laboratory abnormality is considered clinically significant by the local PI and is not otherwise refuted by a repeat test to confirm the abnormality
- The abnormality suggests a disease and/or organ toxicity
- The abnormality is of a degree that requires active management; e.g. change of dose, discontinuation of the drug, more frequent follow-up assessments, further diagnostic investigation, etc.

Hospitalization, Prolonged Hospitalization or Surgery

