9.3.4 Reporting Procedures for Unanticipated Problems and Adverse Events

Participating investigators should notify the local IRB, in an expedited manner, of those events related to study participation that are unforeseen and indicate that participants or others are at increased risk of harm. Researchers should submit reports of the following problems:

- Any AE or UP (regardless of whether the event is serious or non-serious, on-site or off-site) that occurs any time during or after the research study, which in the opinion of the principal investigator is:
 - 1.) Unexpected (An event is “unexpected” when its specificity and severity are not accurately reflected in the protocol-related documents, such as the IRB-approved research protocol, any applicable investigator brochure, and the current IRB-approved informed consent document and other relevant sources of information, such as product labeling and package inserts.)
AND
 - 2.) Related to the research procedures (An event is “related to the research procedures” if in the opinion of the principal investigator or sponsor, the event was more likely than not to be caused by the research procedures.)
AND

- 3.) suggests that the research places subjects or others at a greater risk of harm (including physical, psychological, economic, or social harm) than was previously known or recognized

Serious and unanticipated AEs which are fatal and indicates that participants or others are at increased risk of harm must be reported within 24 hours to the CCC, as well as to the local IRB per their requirements.

Reporting Process

UPs posing risks to subjects or others as noted above will be reported to the local IRB using the institution required form or as a written report of the event (including a description of the event with information regarding its fulfilment of the above criteria, follow-up/resolution and need for revision to consent form and/or other study documentation).

The participating Investigator is expected to report any serious and unexpected adverse experiences, whether or not they are considered related to the CCC, usually within 24 hours.

The participating Investigator is expected to provide as much of the following information as is available to the CCC:

- Protocol name and number
- Subject identifiers
- Demographic data
- Nature of the event
- Severity of the event
- Probable relationship (causality) of AE to study procedure
- Date and time of AE onset

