10.1 Personnel Training

Prior to randomization of the first subject in the study protocol, the PI will ensure that the staff has completed appropriate training and that all documentation including IRB approval is completed and available. The purpose of training is to ensure that study personnel are carrying out the protocol in a consistent way and adhering to good clinical practice guidelines. Staff will have current Human Subjects Training Certification on file. Before enrollment begins, study coordinators and research assistants who will perform the outcome assessments will be trained in all procedures, including completion of the web-based database.

The PI and research staff will constitute the first line of monitoring of the safety of the human participants. Surveillance for AEs will consist of questioning subjects about potential AEs at every study contact, having subjects report any AE to the study team, and having subjects undergo vital sign checks and physical exams during each study visit. Laboratory values will be performed at selected visits and checked.

All study personnel are required to read the consent form and the protocol.

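### Section 9.3.3 ends required adverse-event reporting at Week 14, about 82 days short of 6 months of daily dosing; the last dose is not tied to Visit 4, and completers have no scheduled contact after it

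*Combined protocol and SAP*

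**What the plan says.** **Dosing.** The Study Summary assigns subjects "to receive either letrozole 2.5 mg orally daily or placebo for 6 months". Section 5.2 agrees: "Subjects will take 2.5 mg of Letrozole or an identical placebo by mouth daily for 6 months". Section 3.3 makes participation the same length: "Subjects will participate for 6 months". Sections 5.4 and 6.2 provide a 3-month supply at Baseline and another at Month 3. No section names a stop day or says that dosing ends at Visit 4.

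**AE period.** Section 9.3.3 runs required AE reporting from the first study procedure to the end of treatment follow-up, and then dates that end: "For this study, the end of study treatment follow-up is Week 14". The visit table in 6.3 marks adverse-effect assessment at 1, 3 and 6 months. Section 10.1 gives the method: "Surveillance for AEs will consist of questioning subjects about potential AEs at every study contact".

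**After Visit 4.** The 6-month visit has a window of 30 days either side. Section 6.3 closes the subject's involvement there: "The research coordinator will thank the subject for his or her participation". The one later step is the coordinator's contact with the clinician about laboratory results. For later events, section 9.3.3 relies on an instruction given when the subject is last seen: "the investigator should instruct each subject to report any subsequent event(s) that the subject, or the subject's personal physician, believes might reasonably be related". It also requires unresolved drug-related AEs to be followed, and the sponsor to be told of possibly related deaths or AEs that occur later. Under section 9.3.4 the participating investigator "is expected to report any serious and unexpected adverse experiences, whether or not they are considered related to the CCC". The safety return in 9.4 applies when treatment is permanently withdrawn.

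**The concern.** Safety is a listed secondary endpoint (3.5), and section 8.5 describes this as the first study of letrozole for this indication. The clause that defines when AEs must be reported should therefore cover at least the whole of treatment, and Week 14 does not. Two sites following different parts of the protocol could apply different collection periods to the same endpoint, one stopping in the fourth month and one at Visit 4.

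A second, lesser gap concerns the end of treatment. Active surveillance happens at study contacts, and the last contact for completers is Visit 4. Without a stated stop day, the length of exposure is undefined. Any new event in the days after the last dose is found only if someone volunteers it.

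**Working it through.** **1. Does Week 14 fit 6 months of dosing?** Week 14 = 14 × 7 = day 98. The length of 6 months depends on the convention:

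| Convention | Last day | Days after day 98 | Share of dosing |
|---|---|---|---|
| 30-day months | 180 | 180 − 98 = 82 | 82/180 = 45.6% |
| 26 weeks | 182 | 182 − 98 = 84 | 84/182 = 46.2% |
| Calendar months | 182.6 | 182.6 − 98 = 84.6 | 84.6/182.6 = 46.3% |

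None gives Week 14; 6 months is about Week 26.

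**2. Does Week 14 fit the visits?** With 30-day months, Visit 3 falls on day 90 ± 30 = 60 to 120 and Visit 4 on day 180 ± 30 = 150 to 210. The earliest Visit 4 is 150 − 98 = 52 days after Week 14 and the latest is 210 − 98 = 112 days after it. A Visit 3 held on day 99 to 120 would also fall outside the period.

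**3. Where can the last dose fall?** Assume 90 capsules per supply. With an on-time Visit 3 and full adherence, 180 capsules last to day 180. If Visit 3 is on day 120, the second supply runs to 120 + 90 = day 210. Visit 4 may fall anywhere from day 150 to 210, so the last dose and the visit need not coincide. At the late edge, a day-210 visit after a day-180 last dose takes the primary arterial blood gas (ABG) 30 days off drug. That is 30/2 = 15 half-lives on the 2-day figure in section 1.3.

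**4. Residual exposure after a stop at Visit 4.** Taking five half-lives as the convention, 5 × 2 = 10 days, with 0.5^5 = 3% left. Section 1.3 also gives 2 to 6 weeks to reach steady state. If that is read as five effective half-lives, residual exposure would be 14 to 42 days. The 10-day figure is therefore the low end.

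**5. Events at stake.** Apply the section 1.4 incidences to 10 letrozole subjects and spread them evenly over 180 days. This is an upper guide, because the durations of the source trials are not given.

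| Event | Incidence | Over 180 days | 10 days (× 10/180) | After Week 14 (× 82/180) |
|---|---|---|---|---|
| Myocardial infarction | 0.4% | 0.04 | 0.002 | 0.02 |
| Thromboembolic disorder | 1.1% | 0.11 | 0.006 | 0.05 |
| Pulmonary embolism | up to 2% | 0.20 | 0.011 | 0.09 |
| Fracture | 5.9% to 14.7% | 0.59 to 1.47 | 0.03 to 0.08 | 0.3 to 0.7 |

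The last column would matter only if a site stopped collecting at Week 14.

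**The case against.** The strongest reply is that Week 14 is leftover wording that nobody would follow. Section 9.4 mentions sorafenib, which is not a drug in this trial, so section 9 does appear to carry text from elsewhere. The visit table schedules an adverse-effect assessment at 6 months, section 10.1 requires questioning at each contact, and sections 8.4.3 and 8.7 put all patients in the safety analysis. This stands to a large extent. A reader might infer that 46% of treatment would go unobserved. The documents do not support that, because collection to Visit 4 is the likely practice. The clause is still current text that says when AEs must be reported, and it contradicts the schedule.

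The second reply is that dosing naturally ends by the visit at which participation ends. Nothing is dispensed at Visit 4, and section 5.5 has subjects bring their bottles to each visit. This also stands. A reader might infer gaps of 40 to 70 days (30 to 60 days of remaining capsules plus 10 residual) after a day-150 visit. Those gaps need subjects to go on taking capsules after being thanked and released, and no section provides for that. What remains is that the stop is implied but never stated.

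The third reply is that sections 9.3.3 and 9.3.4 already cover the post-study period. They do require unresolved related events to be followed, and they accept later reports. For new events, however, they are passive. One route depends on the subject or a physician suspecting a link. The other applies to serious, unexpected events once the investigator learns of them. An expected event such as a fracture could escape both.

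Finally, a reader might infer a loss of power for the primary endpoint from ABGs taken off drug. The documents give no rate at which the gradient would revert, and section 1.1 describes vascular remodeling as well as vasodilation. Washout therefore need not mean loss of effect, and no power figure can be supported.

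**Conclusion.** The Week 14 clause is wrong as written. It cannot be reconciled with 6 months of daily dosing or with the 6-month adverse-effect assessment. Read literally, it leaves 82 of 180 treatment days (46%, using 30-day months) outside the required reporting period. The practical effect is probably much smaller, because the rest of the protocol points to collection up to Visit 4.

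The unstated stop day and the absence of any scheduled contact after Visit 4 are lesser points. If dosing stops at Visit 4, about 10 days of residual exposure have only passive reporting, assuming five 2-day half-lives. Very few serious events are expected in that time. The call and the last-dose record are therefore a cheap improvement and not the repair of a serious failing. The sample-size calculation is not affected.

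**What to change.** 1. In 9.3.3, replace Week 14 with an AE collection period that covers all dosing and ends at one telephone AE/SAE contact, made by the existing coordinators after the last dose. Thirty days is a reasonable interval. Ten days is the minimum on the 2-day half-life. Add the call to the visit table and adjust 3.3.
2. In 5.2 and 6.3, state that study drug stops at Visit 4, collect unused capsules there and record the date of the last dose.
3. Keep the existing Visit 4 window. Requiring the visit by about day 180 would remove the later half of the window and risk missed primary measurements in a 20-patient trial. For a late Visit 4, record whether the primary ABG was taken on drug.

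The cost is at most 20 calls, one table row and wording in four sections, with no new procedure. Participation lengthens by about 30 days: to about day 210 for a day-180 last dose, and up to about day 240 if dosing runs to a day-210 visit. Stopping at Visit 4 also makes treatment length vary with the visit date, from as early as day 150, which the present window already allows for the endpoint.
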